#### 9.2.2. Safety Definitions:

#### 9.2.2.1. Adverse Event (AE):

An Adverse Event is defined as any untoward medical occurrence in a patient regardless of its causal relationship to study treatment. An AE can be any unfavorable and unintended sign (including any clinically significant abnormal laboratory test result), symptom, or disease temporally associated with the use of the study treatment, whether or not it is considered to be study drug(s) related. Included in this definition are any newly occurring events and any previous condition that has increased in severity or frequency since the administration of the study.

**Attribution** - the determination of whether an adverse event is related to a medical treatment or procedure.

- Definite the adverse event is clearly related to the investigational agent(s).
- **Probable** the adverse event is likely related to the investigational agent(s).
- **Possible** the adverse event may be related to the investigational agent(s).
- Unlikely The adverse event is doubtfully related to the investigational agent(s).
- Unrelated The adverse event is clearly NOT related to the investigational agent(s)

Medical conditions/diseases present before starting study drugs are only considered adverse events if they worsen after starting the study drug. Abnormal laboratory values or test results constitute adverse events only if they induce clinical signs or symptoms, are considered clinically significant or require therapy.

The severity of the adverse events (AEs) -The severity of the adverse events (AEs) will be graded according to the **National Cancer Institute Common Terminology Criteria for Adverse Events (NCI CTCAE) V**5.0. Events not included in the NCI CTCAE will be scored as follows:

General grading:

- **Grade 1:** Mild: discomfort present with no disruption of daily activity, no treatment required beyond prophylaxis.
- Grade 2: Moderate: discomfort present with some disruption of daily activity, require treatment.
- **Grade 3:** Severe: discomfort that interrupts normal daily activity, not responding to first line treatment.
- Grade 4: Life Threatening: discomfort that represents immediate risk of death

RedCap will be used as the electronic Case Report Form (eCRF). The Investigator (or physician designee) is responsible for verifying and providing source documentation for all adverse events and assigning the attribution for all adverse events for subjects enrolled.

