Adverse events will be captured per the phase II recommended guidelines

 Signs and symptoms relating to adverse event diagnoses will not be captured as individual events. (e.g. event of catheter related infection: redness, pain, swelling

Page | 40 04/25/2024

- at catheter site are signs and symptoms of the catheter related infection and thus will not be recorded as individual events).
- The maximum grade of the adverse event (AE) will be captured per course or protocol defined visit date. The start date will be recorded as when the AE first began or worsened from baseline, regardless of when the event was at its highest grade.
- An AE will be recorded as intermittent if the AE is not continuous but reoccurs at an irregular interval within a course.
- Hematologic adverse events will not be recorded or reported for studies in patients with any type of leukemia and/or related disorders, except for:
  - a. Prolonged myelosuppression as defined by marrow hypocellularity on day 42 or later (6 weeks) from start of therapy without evidence of leukemia (< 5% blasts).
  - b. Hematologic events that result in dose modifications, interruptions or meets the protocol definition of DLT or SAE.
- Abnormal laboratory values or test results will not be recorded or reported as adverse events unless it leads to therapeutic intervention, results in dose modification or interruption, or meets the protocol definition of a DLT or SAE.

Only the following AEs from the Adverse Event Record will be reported in the CRF:

- Any grade adverse event that is possibly, probably, or definitely related to the study drug(s).
- All serious adverse events regardless of attribution to the study drug(s).
- Any grade adverse event regardless of attribution to the study drug(s) that results in any dose modification.

The investigator (or physician designee) is responsible for verifying and providing source documentation for all adverse events and assigning the attribution for all adverse events for subjects enrolled. For non-MD Anderson laboratory results, the principal investigator (or physician designee) will review laboratory results, and sign and date the results.

Table 17: Recommended Adverse Event Recording Guidelines

Attribution	Grade 1	Grade 2	Grade 3	Grade 4	Grade 5
Unrelated	Phase I	Phase I	Phase I Phase II	Phase I Phase II Phase III	Phase I Phase II Phase III
Unlikely	Phase I	Phase I	Phase I Phase II	Phase I Phase II Phase III	Phase I Phase II Phase III

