- Death or life-threatening events that are unexpected, possibly, probably or definitely related to drug must be reported (initial or follow up) to the IND Sponsor within 24 hours of knowledge of the event
- Additionally, any serious adverse events that occur after the 30-day time period
  that are related to the study treatment must be reported to the INDSponsor. This
  may include the development of a secondary malignancy.
- The electronic SAE application (OnCore) will be utilized for safety reporting to the IND Sponsor and MD Anderson IRB.

Page | 42 04/25/2024

• All events reported to the supporting company must also be reported to the INDSponsor.

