#### 12. STATISTICAL CONSIDERATIONS

This is a phase II open-label single arm and single institution clinical trial to evaluate the efficacy and safety of CB-103 in combination with venetoclax in adolescent and adult patients with T-ALL/T-LL in first or second bone marrow recurrence refractory to initial induction therapy or refractory to at least one reinduction attempt. Up to 30 patients may be enrolled, without regard to Notch status; we anticipate that approximately 50% of these patients will be Notch positive. The primary efficacy endpoint of the study is overall response rate (ORR, including CR,CRi and PR rate) after the first two induction cycles, and the primary toxicity endpoint is the rate of toxic events, defined as a grade ≥3 non-haemtological AEs that are possibly or probably related to the study drugs (see Adverse Events (SAE) definition in section 9.2.2.1.) occurring during the 28 days of induction cycle.

We simultaneously monitor efficacy and toxicity using the Bayesian optimal phase 2 (BOP2) design [32]. Specifically, let n denote the interim sample size, and N denote the maximum sample size. Let  $Y_{eff}$  and  $Y_{tox}$  denote the binary efficacy and toxicity endpoints, with  $Y_{eff} = 1$  and  $Y_{tox} = 1$  indicating that patients experience efficacy and toxicity, respectively. We assume that the joint distribution of  $(Y_{eff}, Y_{tox})$  follows a multinomial distribution with four elementary outcomes:  $(Y_{eff}, Y_{tox}) = (1, 1), (1, 0), (0, 1)$  and (0, 0). Let  $\mathbf{p} = (P_{11}, P_{10}, P_{01}, P_{00})$  denote the probabilities of observing the four outcomes, and let  $P_{eff} = Pr(Y_{eff} = 1), P_{tox} = Pr(Y_{tox} = 1)$  and  $P_{efftox} = Pr(Y_{eff} = 1, Y_{tox} = 1)$ . When efficacy and toxicity endpoints are monitored separately, the joint distribution reduced to marginal distribution of efficacy and marginal distribution of toxicity, respectively.

The treatment is deemed unacceptable if  $p_{eff} \le 0.15$  or  $p_{tox} > 0.20$ . Thus, we will stop enrolling patients and claim that the treatment is unacceptable if

$$Pr(p_{eff} > 0.15|data) < \lambda \left(\frac{n}{N}\right)^{\alpha}$$

or

$$Pr(p_{tox} \le 0.20|data) < \lambda \left(\frac{n}{N}\right)^{\alpha/3},$$

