where  $\lambda$ =0.57 and  $\alpha$ =0.86 are design parameters optimized to maximize the study power, i.e., probability of correctly concluding an efficacious and safe **treatment as acceptable** when  $p_{eff}=0.3$ ,  $p_{tox}=0.10$  and  $p_{efftox}=0.05$ , while controlling that the probability of incorrectly claiming an inefficacious and toxic treatment, i.e., type I error, with  $p_{eff}=0.15$ ,  $p_{tox}=0.20$  and  $p_{efftox}=0.05$ , to 8.3%. Note that in the safety stopping rule, the original publication of the design used the probability cutoff  $\lambda(n/N)^{\alpha}$ , here the attenuation factor 3 is added (i.e.,  $\alpha/3$ ) to obtain stricter interim stopping boundaries to enhance safety.

This optimization is performed assuming a vague Dirichlet prior Dir(0.05,0.1,0.15,0.7) for p. The prior is chosen such that it corresponds to a prior effective sample size of 1 patient, and the prior estimates of p\_eff and p\_tox match the values specified when the treatment is unacceptable. The above decision rule leads to the following optimal stopping boundaries:

Table 18: Optimized stopping boundaries

# patients treate	d Stop if # response <=	OR # toxicity >=
10	0	3
20	2	5
30	5	6

When the total number of patients reaches the maximum sample size of 30, we conclude that the treatment is acceptable if the number of responses are greater than 5, and the number of toxicities are less than 6; otherwise we conclude that the treatment is unacceptable. The go/no-go criteria in Table 18 are non-binding.

Below (**Table 19**) are the operating characteristics of the design based on 10000 simulations using the BOP2 web application (BOP2 V1.4.10.0), which is available at http://www.trialdesign.org.

Table 19: Operating characteristics

Scenario	Pr(Eff)	Pr(Tox)	Pr(Eff & Tox)	Early Stopping (%)	Claim Acceptable (%)	Average Sample Size
1	0.30	0.2	0.05	48.77	33.34	21.7
2	0.15	0.3	0.05	89.47	1.56	14.2
3	0.30	0.1	0.05	14.26	77.76	27.6
4	0.15	0.1	0.05	51.07	20.83	22.3
5	0.30	0.2	0.10	49.39	31.94	21.6
6	0.15	0.2	0.05	71.48	8.34	18.2
7	0.20	0.1	0.05	31.75	45.19	25.1
8	0.15	0.4	0.06	97.62	0.19	11.6
9	0.40	0.1	0.06	9.74	86.76	28.3
10	0.40	0.4	0.16	96.03	0.50	12.1

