Upon completion of the trial, efficacy (per ORR and toxicity rates will be summarized as proportions with corresponding 95% Agresti-Coull confidence intervals. Given 30 patients, the following table (**Table 20**) provides rates and confidence intervals over a range of incidences:

Table 20: Rates and Confidence Intervals

Incidence	Proportion (95% CI)
0/30	0 (0, 0.13)
1/30	0.03 (0, 0.18)
2/30	0.07 (0.01, 0.22)
3/30	0.1 (0.03, 0.26)
4/30	0.13 (0.05, 0.3)
5/30	0.17 (0.07, 0.34)
6/30	0.2 (0.09, 0.38)
7/30	0.23 (0.12, 0.41)

Protocol 2021-0547
Page | 51 04/25/2024

8/30       0.27 (0.14, 0.45)         9/30       0.3 (0.17, 0.48)         10/30       0.33 (0.19, 0.51)         11/30       0.37 (0.22, 0.55)         12/30       0.4 (0.25, 0.58)         13/30       0.43 (0.27, 0.61)         14/30       0.47 (0.3, 0.64)         15/30       0.5 (0.33, 0.67)         16/30       0.53 (0.36, 0.7)         17/30       0.57 (0.39, 0.73)         18/30       0.6 (0.42, 0.75)         19/30       0.63 (0.45, 0.78)         20/30       0.67 (0.49, 0.81)         21/30       0.7 (0.52, 0.83)         22/30       0.73 (0.55, 0.86)         23/30       0.77 (0.59, 0.88)         24/30       0.8 (0.62, 0.91)         25/30       0.87 (0.7, 0.95)         27/30       0.9 (0.74, 0.97)         28/30       0.93 (0.78, 0.99)         29/30       0.97 (0.82, 1)         30/30       1 (0.87, 1)		
10/30       0.33 (0.19, 0.51)         11/30       0.37 (0.22, 0.55)         12/30       0.4 (0.25, 0.58)         13/30       0.43 (0.27, 0.61)         14/30       0.47 (0.3, 0.64)         15/30       0.5 (0.33, 0.67)         16/30       0.53 (0.36, 0.7)         17/30       0.57 (0.39, 0.73)         18/30       0.6 (0.42, 0.75)         19/30       0.63 (0.45, 0.78)         20/30       0.67 (0.49, 0.81)         21/30       0.7 (0.52, 0.83)         22/30       0.73 (0.55, 0.86)         23/30       0.77 (0.59, 0.88)         24/30       0.8 (0.62, 0.91)         25/30       0.83 (0.66, 0.93)         26/30       0.87 (0.7, 0.95)         27/30       0.9 (0.74, 0.97)         28/30       0.93 (0.78, 0.99)         29/30       0.97 (0.82, 1)	8/30	0.27 (0.14, 0.45)

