25/30     0.83 (0.66, 0.93)       26/30     0.87 (0.7, 0.95)       27/30     0.9 (0.74, 0.97)       28/30     0.93 (0.78, 0.99)       29/30     0.97 (0.82, 1)	23/30	0.77 (0.59, 0.88)
26/30     0.87 (0.7, 0.95)       27/30     0.9 (0.74, 0.97)       28/30     0.93 (0.78, 0.99)       29/30     0.97 (0.82, 1)	24/30	0.8 (0.62, 0.91)
27/30     0.9 (0.74, 0.97)       28/30     0.93 (0.78, 0.99)       29/30     0.97 (0.82, 1)	25/30	0.83 (0.66, 0.93)
28/30 0.93 (0.78, 0.99) 29/30 0.97 (0.82, 1)	26/30	0.87 (0.7, 0.95)
29/30 0.97 (0.82, 1)	27/30	0.9 (0.74, 0.97)
	28/30	0.93 (0.78, 0.99)
30/30 1 (0.87, 1)	29/30	0.97 (0.82, 1)
	30/30	1 (0.87, 1)

In secondary analysis, ORR will be summarized separately by Notch status as proportions with corresponding 95% Agresti-Coull confidence intervals. The difference in ORR between Notch groups will be assessed by Fisher's exact test.

Other measures of response (CR, Cri, PR, relapse, radiographic tumor response, CNS remission, CNS relapse) and minimal residual disease (MRD) will be summarized as proportions with corresponding 95% Agresti-Coull confidence intervals.

Duration of Response (DoR), Overall Survival (OS), and event-free Survival (EFS) will be summarized using Kaplan-Meier methods.

In exploratory analyses, correlations between ORR and pharmacokinetic and pharmacodynamics markers will be summarized. Rates of patients transitioning to Hematopoietic stem cell transplant (HSCT) will be summarized. Endpoints may be further summarized separately by Notch status.

Additional statistical methods may be used.

The Investigator is responsible for completing an efficacy/safety summary reports and submitting it to the IND Office Medical Affairs and Safety Group, for review and approval.

This should be submitted after the first 10 evaluable patients complete 1 cycle of study treatment, and every 10 evaluable patients, thereafter. Efficacy summary will be submitted for every 10 evaluable patients after they complete 2 cycles of therapy.

Page | 52 04/25/2024

A copy of the safety summary report should be placed in the Investigator's Regulatory Binder under "sponsor correspondence".

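### As worded, the primary toxicity endpoint leaves out events rated Definite, so a patient whose only qualifying event is definitely drug-related counts as non-toxic

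*Combined protocol and SAP*

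**What the plan says.** Section 12 makes the rate of toxic events a primary endpoint and defines such events as "grade ≥3 non-haemtological AEs that are possibly or probably related to the study drugs", with the window "occurring during the 28 days of induction cycle". It refers the reader to section 9.2.2.1 for the adverse event definition.

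Section 9.2.2.1 sets out five attribution levels: Definite, Probable, Possible, Unlikely and Unrelated. Definite is the level at which "the adverse event is clearly related to the investigational agent(s"); Probable and Possible are defined separately, as weaker degrees of relatedness. Table 17 also gives the top level a row of its own.

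Two other rules use all three related levels:

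- the case report form rule in 9.2.2.1: "Any grade adverse event that is possibly, probably, or definitely related to the study drug(s");
- the 24-hour rule in 9.2.2.2: "Death or life-threatening events that are unexpected, possibly, probably or definitely related to drug must be reported".

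The toxicity count enters the plan in three places, all in Section 12: the Table 18 boundaries (stop at 3 or more of 10, 5 or more of 20, 6 or more of 30), the final rule (acceptable only with more than 5 responses and fewer than 6 toxicities), and the toxicity proportion with its 95% Agresti-Coull interval. Section 12 adds that "The go/no-go criteria in Table 18 are non-binding".

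**The concern.** An endpoint built from two of the three related levels drops the events for which the causal link is clearest. The error runs one way: omitting Definite events can lower the toxicity count but never raise it. The count feeds a safety rule whose interim cutoff the protocol says was deliberately tightened (the exponent divided by 3), so an undercount works against that aim. Anyone deriving the toxicity variable from the text would select the two named levels and obtain a count that can sit below the boundary when the real one is on or above it.

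**Working it through.** **1. Is Definite brought in anywhere?** Section 12 names Possible and Probable. The section it refers to keeps Definite apart from both. The two passages that mean all related events list three levels. No sentence says that Probable includes Definite, or that Definite events count toward the toxicity variable. The cross-reference therefore does not close the gap.

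**2. Reproducing the plan's rule.** Inputs from Section 12: prior Dir(0.05, 0.1, 0.15, 0.7), which gives a Beta(0.20, 0.80) marginal for toxicity; λ = 0.57; α = 0.86; N = 30. Stop if Pr(p_tox ≤ 0.20 | x of n) < 0.57 × (n/30)^(0.86/3).

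| n | Cutoff | Last count that continues | First count that stops |
|---|---|---|---|
| 10 | 0.416 | 2 (posterior 0.561) | 3 (0.272) |
| 20 | 0.507 | 4 (0.544) | 5 (0.331) |
| 30 | 0.570 | 5 (0.713) | 6 (0.536) |

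These are the Table 18 toxicity boundaries. Exact enumeration of the full rule, with looks at 10, 20 and 30, gives these chances of claiming acceptable: 33.6% in scenario 1 (Table 19 prints 33.34), 1.56% in scenario 2 (1.56), 78.5% in scenario 3 (77.76) and 8.2% in scenario 6 (8.34).

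**3. One patient at the boundary.** This needs the wording to be applied literally and the true count to lie exactly on the boundary, but no assumed rates.

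- Final analysis: 6/30 = 0.20 (0.09 to 0.38), unacceptable, becomes 5/30 = 0.17 (0.07 to 0.34), acceptable if responses exceed 5.
- First look: 3/10 (stop) becomes 2/10 (continue).

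**4. Operating characteristics under assumed shares.** Let s be the share of qualifying events rated Definite and k the number of qualifying events per toxic patient, attributed independently. A toxic patient is missed only if all k events are Definite, so the counted rate is q = true rate × (1 − s^k). The documents give neither s nor k; I take s = 10%, 25%, 40% and k = 1 (worst case) or 2 (milder). First-look stopping for toxicity is P(Bin(10, q) ≥ 3). Claiming acceptable is by exact enumeration, with response rate 30% and response independent of toxicity.

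True toxicity rate 30%:

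| k | s | Counted rate q | First-look stop for toxicity | Claim acceptable |
|---|---|---|---|---|
| – | 0 | 30% | 61.7% | 5.7% |
| 1 | 10% | 0.30 × 0.90 = 27.0% | 53.4% | 10.6% |
| 1 | 25% | 0.30 × 0.75 = 22.5% | 39.8% | 23.2% |
| 1 | 40% | 0.30 × 0.60 = 18.0% | 26.3% | 42.6% |
| 2 | 10% | 0.30 × 0.99 = 29.7% | 60.9% | 6.0% |
| 2 | 25% | 0.30 × 0.9375 = 28.1% | 56.6% | 8.4% |
| 2 | 40% | 0.30 × 0.84 = 25.2% | 48.0% | 14.8% |

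For k = 1, the chance that a first-look boundary is truly crossed but missed is the sum over x = 3 to 10 of P(Bin(10, 0.30) = x) × P(Bin(x, 1 − s) ≤ 2), which gives 8.4%, 21.9% and 35.4%.

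At a true rate of 40%, claiming acceptable rises from 0.4% to 1.3%, 5.7% or 18.2% (k = 1), or to 0.5%, 0.9% or 2.4% (k = 2).

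**5. The plan's own null (scenario 6: response 0.15, toxicity 0.20, joint 0.05).** If 10% or 20% of toxic patients had only a Definite event, so that the toxicity and joint probabilities are multiplied by 0.9 or 0.8, claiming acceptable would rise from 8.2% to 10.9% or 14.0%, against the stated control at 8.3%.

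**The case against.** The strongest reply is that nobody would apply the wording this way. Naming Possible and Probable reads naturally as a minimum degree of attribution; counting a possible event while ignoring a certain one makes no sense in a safety rule; and the cross-referenced section uses all three levels for data capture. Section 9.2.1 also plans a primary safety analysis of adverse events with no limit on attribution level, so Definite events would be reported there. They are recorded on the case report form, serious ones are reported, safety summaries go for review ("This should be submitted after the first 10 evaluable patients complete 1 cycle of study treatment", then every 10 evaluable patients), and Table 18 is non-binding. The larger percentages combine an assumed high share of Definite events with the one-event worst case. In the mildest case the effect is negligible, 5.7% to 6.0%. At the design's target toxicity rate of 10%, claiming acceptable is the right conclusion anyway.

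Much of this stands. The slip is probably unintended, the practical risk is limited, and the percentages are conditional illustrations rather than estimates. It does not answer the point about the endpoint itself. Section 9.2.1 does not redefine the count that meets the boundaries, and neither recording, reporting nor periodic review puts Definite events into that count, the final rule or the toxicity proportion. A primary endpoint should not depend on the analyst reading past its text.

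**Conclusion.** The concern holds. As written, the endpoint omits the Definite level, and no other text restores it. Under a literal reading one patient is enough to reverse the final conclusion or the first-look decision when the true count is on the boundary. Over the assumed range, a true 30% toxicity rate is understated by 0.3 to 12 percentage points (30 − 29.7 to 30 − 18), and the chance of claiming acceptable goes from 5.7% to between 6.0% and 42.6%. Those figures rest on assumed Definite shares, one or two independently attributed events per toxic patient, response independent of toxicity, and the non-binding rule being followed. If the team already counts Definite events, the effect is nil. It should be corrected because it is the operative definition of a primary endpoint; the case does not depend on the simulated percentages.

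**What to change.** In the Section 12 endpoint definition, name all three related levels, so that it covers events possibly, probably or definitely related to the study drugs, in line with 9.2.2.1 and 9.2.2.2. Check any interim toxicity count already made against that definition, and correct the corresponding summary report if it changes.

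The cost is one word and that recheck. The events are already on the case report form, so no new data are needed. Table 18, the sample size and Table 19 are unchanged, because they were computed for a toxicity rate without regard to attribution level. The counted toxicity rate may turn out higher than under the present wording.

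### Section 12 makes the stopping rule mandatory and also calls it non-binding, while the 8.3% type I error and Table 19 hold only if every interim stop is obeyed

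*Combined protocol and SAP*

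**What the plan says.** All the relevant text is in section 12, Statistical Considerations, of the combined protocol and SAP.

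- **The rule.** After defining the unacceptable region, the plan says "we will stop enrolling patients and claim that the treatment is unacceptable if" either posterior probability falls below its cutoff. This is written as an obligation.
- **The boundaries.** Table 18 gives them at 10, 20 and 30 patients: stop at 0, 2 or 5 responses or fewer, or at 3, 5 or 6 toxicities or more.
- **The final decision.** At 30 patients the treatment is acceptable with more than 5 responses and fewer than 6 toxicities; "otherwise we conclude that the treatment is unacceptable".
- **The status of the boundaries.** The next sentence reads "The go/no-go criteria in Table 18 are non-binding". It does not separate the interim rows from the 30-patient row.
- **The error rate.** The design is described as "controlling that the probability of incorrectly claiming an inefficacious and toxic treatment, i.e., type I error", at response 0.15, toxicity 0.20 and joint probability 0.05, to 8.3%.
- **The operating characteristics.** The figures in Table 19 "are the operating characteristics of the design based on 10000 simulations using the BOP2 web application". Nothing says how a crossed boundary was treated in those simulations.
- **Oversight.** Efficacy and safety summaries are due for every 10 evaluable patients, the investigator "submitting it to the IND Office Medical Affairs and Safety Group, for review and approval". The text does not say whether a crossed boundary may be overridden, by whom, or on what grounds.

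**The concern.** The two statements give different instructions for the same event. If the tenth patient brings the toxicity count to 3, one sentence requires enrolment to stop and the other makes stopping optional. The reviewing group cannot tell from the plan which applies.

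The difference also affects the numbers. If continuing past a boundary is allowed, some trials that would have stopped go on to 30 patients, and some of those meet the final criteria. The probability of claiming acceptable therefore rises whether the treatment is poor or good. Early stopping falls and more patients are treated. Error rates, power, early-stopping rates and mean sample sizes computed with obeyed stops then do not describe the declared design.

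Because the non-binding sentence covers the whole of Table 18, it can be read as reaching the 30-patient decision. On that reading no type I error is defined, since nothing fixes when the treatment is claimed acceptable.

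**Working it through.** **Inputs (section 12).** Maximum 30 patients; λ = 0.57, α = 0.86, with α/3 in the safety rule; prior Dir(0.05, 0.1, 0.15, 0.7); Table 18 boundaries; Table 19 scenarios with their joint probabilities; 10,000 simulations.

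**Step 1: reproduce Table 18.** The Dirichlet prior has margins Beta(0.05 + 0.10, 0.15 + 0.70) = Beta(0.15, 0.85) for response and Beta(0.05 + 0.15, 0.10 + 0.70) = Beta(0.20, 0.80) for toxicity. With x events in n patients, the posteriors are Beta(0.15 + x, 0.85 + n − x) and Beta(0.20 + x, 0.80 + n − x). The cutoffs are 0.57(n/30)^0.86 for response and 0.57(n/30)^(0.86/3) for toxicity. The boundaries obtained are:

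| n | Stop if responses ≤ | or toxicities ≥ |
|---|---|---|
| 10 | 0 | 3 |
| 20 | 2 | 5 |
| 30 | 5 | 6 |

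This is Table 18 exactly.

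**Step 2: reproduce Table 19 with all stops obeyed.** Each block of 10 patients is multinomial with cell probabilities P11 = joint, P10 = P_eff − joint, P01 = P_tox − joint, P00 = the remainder. I enumerated all outcomes over three blocks, removing at 10 and 20 patients every path that meets a boundary.

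| Scenario (response/toxicity/joint) | Claim acceptable, exact (printed) | Early stop, exact (printed) | Mean n, exact (printed) |
|---|---|---|---|
| 6 (0.15/0.20/0.05) | 8.17% (8.34%) | 71.66% (71.48%) | 18.14 (18.2) |
| 4 (0.15/0.10/0.05) | 21.03% (20.83%) | 51.01% (51.07%) | 22.26 (22.3) |
| 3 (0.30/0.10/0.05) | 78.46% (77.76%) | 13.97% (14.26%) | 27.63 (27.6) |
| 1 (0.30/0.20/0.05) | 33.60% (33.34%) | 48.22% (48.77%) | 21.78 (21.7) |

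The claim-acceptable rates in all ten scenarios agree within about 2 simulation standard errors.

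**Step 3: override the interim stops and keep the 30-patient rule.** The plan does not define overriding, so ignoring every stop is an assumed worst case.

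| Scenario | Stops obeyed | All interim stops overridden |
|---|---|---|
| 6 (type I error point) | 8.17% | 10.42% |
| 4 | 21.03% | 24.88% |
| 3 (power point) | 78.46% | 85.31% |

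Partial overrides at scenario 6 give 8.7% (20-patient look ignored), 8.94% (futility stops ignored), 9.5% (10-patient look ignored) and 9.57% (toxicity stops ignored).

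**Step 4: which version was printed?** The simulation standard error at 8.34% is √(0.0834 × 0.9166 / 10,000) = 0.28 points. The no-stopping value lies (10.42 − 8.34)/0.28 ≈ 7 standard errors away. The smallest partial override, 8.7%, could not be excluded on this figure alone, but the early-stopping column settles it. In scenario 6 the stopping probability is 0.4693 at 10 patients and 0.2472 at 20. Both looks are needed to reach the printed 71.48%, and mean n is then 10(0.4693) + 20(0.2472) + 30(0.2834) ≈ 18.1. Without the second look only 46.9% would stop early.

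**Step 5: exposure.** With all stops overridden, early stopping is 0% and n is 30 in every scenario. In scenario 6 that is 30 − 18.1 ≈ 12 more patients on average. In scenario 8 (response 0.15, toxicity 0.40), where Table 19 prints 97.62% early stopping and a mean of 11.6, it is 30 − 11.6 ≈ 18 more.

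**The case against.** **Non-binding rules are common in phase II, and the shift is small.** Both are true. The 10.4% requires every futility and every toxicity stop to be overridden; partial overrides stay between 8.7% and 9.6%, power rises too, and enrolment stays within the cap ("Up to 30 patients may be enrolled, without regard to Notch status"). This limits the size of the point. It does not remove the contradiction, and a plan that allows overriding should not quote only the rate that assumes none.

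**The final rule stands on its own.** The 30-patient decision has an unqualified sentence, and no enrolment is left to stop then. That is a fair reading, but the row is in Table 18 and the next sentence covers the table without exception.

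**Oversight exists.** Besides the reporting in section 12, section 10.3 mentions review of the protocol by the institution's DSMC, and section 10.5 reserves the investigators' right to terminate. Neither says who may override a boundary.

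**A stronger reading: the 8.3% hides larger one-endpoint errors.** A reader might infer this because "The treatment is deemed unacceptable if" either endpoint fails, whereas the 8.3% is for both at their limits. The documents do not support calling it an error. Section 12 gives the exact point for the 8.3% and does not call it a maximum, and Table 19 prints the one-endpoint rates: 20.83% in scenario 4, and 33.34% and 31.94% in scenarios 1 and 5. Those last two are boundary cases, because toxicity of exactly 0.20 is not above 0.20. At most a row label is missing. A general sentence on such rates would be hard to word safely, since they depend on the other endpoint: at a response rate of 15% under independence, the rate is 23.4% at 10% toxicity, 26.3% at 5% and 26.7% near zero.

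**Conclusion.** The point holds as a contradiction within section 12 and an unstated assumption behind its operating characteristics. The 8.3% and Table 19 are correctly computed for a design whose interim stops are all obeyed; they are not assured for the non-binding design that the text declares.

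The effect on the labelled error is modest: at most about 2.3 points (10.42 − 8.17) at the type I error point. The effect on early stopping and patient exposure is larger.

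These sizes assume looks at exactly 10 and 20 patients with outcomes known, the printed joint probabilities, and the 30-patient rule kept. If that rule may also be overridden, no error rate can be given. A reader might also infer that Table 19 is wrong or that the boundaries were miscalculated; both reproduce, so that inference fails. This should be corrected, but it calls for no redesign.

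**What to change.** 1. Reconcile the mandatory stopping sentence with the non-binding sentence. Which one stands is the sponsor's decision.
2. Say whether non-binding status covers the 30-patient row.
3. State that the 8.3% and every column of Table 19 assume that all interim stops are obeyed.
4. If the stops stay non-binding, print the figures with no interim stopping and the 30-patient rule kept: type I error 10.4%, scenario 4 24.9%, power 85.3%, n = 30. Also name who decides on an override within the existing 10-patient review by the IND Office group.
5. Optionally, mark which Table 19 rows fall in the unacceptable region as section 12 defines it.

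**Cost.** Wording only: no boundary, sample size or printed Table 19 figure changes. With non-binding stops the stated error rate looks slightly less favourable. With binding stops, discretion at the interim looks is lost.
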